# Analysis of post-treatment adverse events

- All post-treatment AEs by primary SOC and PT, sorted by the internationally agreed SOC order and decreasing incidence of PTs within each SOC;
- All post-treatment SAEs by primary SOC and PT, sorted by the sorting order defined above;

# Subgroup of patients with two consecutive LDL-C <25 mg/dL

If applicable, similar summaries of TEAEs as those described above will be also provided on the safety subgroup population of patients with two consecutive results of calculated LDL-C <25 mg/dL (as defined in Section 2.1.5) during the current study. Only TEAE for which it will be confirmed or unclear that they occurred, worsened or became serious the day or after the first level of LDL-C <25 mg/dL will be considered.

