	 Values and percent changes from baseline of the parent study in other lipids and other lipoproteins, including total cholesterol, non- high-density lipoprotein cholesterol (non-HDL-C), HDL-C, triglycerides (TGs), apolipoprotein (Apo) B, ApoA-1, ApoB/ApoA-1 ratio and Lp(a) over time in this study. 					
	Other Endpoints:					
	Anti-alirocumab antibodies assessed throughout the study.					
	 Proportion of patients who were up-titrated to 150 mg of alirocumab based on Investigator's judgment. 					
	 Proportion of patients who were down-titrated to 75 mg of alirocumab based on Investigator's judgment. 					
	 Reasons (ie, LDL-C threshold, AE) that trigger a down-titration or an up-titration of alirocumab. 					
	EQ-5D summary scores.					

ASSESSMENT SCHEDULE

Patient assessments in the OLE period

- Day 1 / Week 0 (End of treatment visit of the parent double-blind study = OLE Visit 1, except for the patients having participated in the LTS11717).
- Complete study visits: Patients will be assessed in the clinic at Weeks 4 (Visit 2), 8 (Visit 3), 12 (Visit 4), 24 (Visit 5), and then every 24 weeks until EOT Visit (Visit 17), or early termination.
- IMP dispensing visits: From Week 24, until study completion IMP dispensing visits will be scheduled every 12 weeks, in-between the clinic visits in order to allow for dispensing IMP.

Patient assessments in the FU period

 A follow up call, Visit 18, will be planned 10 weeks after the last IMP injection, ie 8 weeks after the EOT visit, for the patients who will complete the study and for the patients who will early discontinue whatever the reason.

STATISTICAL CONSIDERATIONS

Sample size determination:

As this study is an open-label extension planning to include patients from previous studies, no calculation for sample size was performed. It is expected to enroll up to 1,200 heFH patients based on the number of patients already enrolled in the parent studies.

Analysis Population:

Safety analyses will be performed on Safety population which consists of patients receiving at least one dose or partial dose of IMP in the current study.

Efficacy analyses will be performed on patients receiving at least one dose or partial dose of IMP in the current study, with a baseline (from parent study) LDL-C available and with at least one LDL-C value available in the period from first IMP injection in the current study to last IMP injection + 21 days.

Analysis of safety endpoints:

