10.1.1.3 Visit 3/ Week 8 (Day 57 ± 7)

- Collect adverse events
- Record concomitant medication
- Take vital signs including heart rate and blood pressure
- Data collection on IMP administration and IMP compliance check by review of diary
- Obtain fasting blood sample for:
 - Lipids: measure or calculation of total-C, LDL-C, HDL-C, TG, non-HDL-C
 - Hematology
 - Chemistry
 - CPK
 - Liver panel
- From week 8 onwards, lipid parameters will be unblinded and communicated to the investigator in real time.
- Local urine pregnancy test (females of childbearing potential only).
- Reminders
 - An appointment will be given for the next visit.
 - Patient to bring the diary and used kits and unused auto-injectors at the next visit.
 - Remind patient to be in fasting conditions (ie, overnight, at least 10-12 hours fast and refrain from smoking) for next visit. Also, alcohol consumption within 48 hours and intense physical exercise within 24 hours preceding the next visit are discouraged.

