10.1.1.5 Visit 5/ Week 24 (Day 169 ± 7)

- Collect adverse events
- Record concomitant medication
- Take vital signs including heart rate and blood pressure
- Get body weight measurement
- Physical examination
- Data collection on IMP administration and IMP compliance check by review of diary and treatment kit
- Obtain fasting blood sample for:
 - Lipids: measure or calculation of total-C, LDL-C, HDL-C, TG, non-HDL-C
 - Hematology
 - Chemistry
 - CPK
 - Liver panel
 - Anti-alirocumab antibodies
 - -
- Local urine pregnancy test (females of childbearing potential only).

- Completion of EQ-5D questionnaire by patient
- IVRS/IWRS contact for allocation of a batch number for treatment kit
- IMP kit dispensation and treatment administration package should be provided. The patient injection instruction manual and diary may be given, as needed.
- Reminders
 - An appointment will be given for the next visit.
 - Patient to bring the diary and used kits and unused auto-injectors at the next visit.

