### Observation period

The period of safety observation starts from the time when the patient gives informed consent and is divided into the following periods:

- The PRE-TREATMENT period: defined as the time from the signed informed consent date up to the time of first dose of alirocumab in the OLE study. The adverse events occurring during this period were to be reported and recorded in the parent study database. However, after the lock of parent study database, some exceptional pre-treatment adverse events have been recorded in the OLE study database with a start date in the parent study period.
- The treatment-emergent adverse event (TEAE) period: defined as the time from the first dose of alirocumab in the OLE study up to the day of last dose of alirocumab received in the OLE study + 70 days (10 weeks), as residual effect of alirocumab is expected until 10 weeks after the stop of alirocumab.

The TEAE period will include:

- The TREATMENT period defined as the time from the first dose of alirocumab in the OLE study up to the day of last dose of alirocumab received in the OLE study + 21 days.
- The POST-TREATMENT period: defined as the time starting the day after the end of TEAE period up to the end of study

The on-study observation period is defined as the time from first dose of alirocumab in the OLE study until the last protocol planned visit of the patient in the OLE study. The last protocol planned visit is defined as the safety follow-up call if done, else 10 weeks after last injection of alirocumab.

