#### 2.1.5 Other variables

Other assessment variables listed below are defined using same definitions and rules as for calculated LDL-C, when applicable (see Section 2.1.3).

- The proportion of patients with two consecutive (spaced out by at least 21 days) calculated LDL-C <25 mg/dL (<0.65 mmol/L) (respectively two consecutive calculated LDL-C <15 mg/dL,i.e. < 0.39 mmol/L) during the OLE treatment period.
- For the patients with two consecutive results as described above, the time from the first study treatment administration in OLE study to the first calculated LDL-C<25 mg/dL (respectively, calculated LDL-C <15 mg/dL for these patients).

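### The low-LDL-C safety subgroup counts adverse events from the first value <25 mg/dL but admits patients only on a second, usually due 16 or 24 weeks later, so it understates deaths and, to an unknown lesser degree, discontinuations

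*SAP*

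**What the plan says.** SAP 2.4.5.1 provides, if applicable, for the TEAE summaries to be repeated in "the safety subgroup population of patients with two consecutive results of calculated LDL-C <25 mg/dL". On timing, only TEAEs that "occurred, worsened or became serious the day or after the first level of LDL-C <25 mg/dL will be considered", together with those whose timing is unclear. SAP 2.1.5 defines the pair as "two consecutive (spaced out by at least 21 days) calculated LDL-C <25 mg/dL" during the OLE treatment period, which SAP 2.1.4 runs "up to the day of last dose of alirocumab received in the OLE study + 21 days".

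Protocol 1.2 and 10.1.1 schedule on-treatment LDL-C at Week 8, at Week 24 and every 24 weeks after that; no lipids are drawn at Weeks 4 and 12. The synopsis describes complete visits at Weeks 4, 8, 12 and 24 "and then every 24 weeks until EOT Visit (Visit 17" or early termination.

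The repeated summaries include TEAEs leading to death, TEAEs leading to permanent discontinuation and event rates per patient-year.

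**The concern.** Membership depends on a later laboratory result, while the event clock starts at an earlier one. Between the two dates a member cannot, by definition, have died. This is immortal-time selection.

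The interval is not short. The 21-day minimum is far below the scheduled spacing of lipid samples, and things can happen in between. Investigators receive lipid values in real time from Week 8 (Protocol 8.3), and SAP 2.4.3.1 allows 3 days for a calculated central-laboratory value to reach them. From Week 12 the dose may be changed on the LDL-C from the previous scheduled visit (Protocol 8.4), and dispensing visits at Weeks 12, 36, 60 and so on precede the next lipid sample.

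Safety is the primary objective, and no other planned table relates adverse events to very low LDL-C. SAP 2.1.5 and 2.4.6 count and time the lipid event itself, and the time-to-event analysis in 2.4.6 leaves out patients with only one post-baseline result. SAP 2.4.3.1 describes titration by LDL-C category but does not tabulate TEAEs. Death and discontinuation are also the outcomes most closely tied to never having a second low value.

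**Working it through.** **Inputs**

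- Visit days, from the section titles in Protocol 10.1.1: "Visit 3/ Week 8 (Day 57 ± 7", "Visit 5/ Week 24 (Day 169 ± 7", then Days 337, 505, 673, 841, 1009 and 1177, each ± 7 days.
- End of TEAE period: last dose + 70 days (SAP 2.1.4). A completer has the EOT visit at Week 168, 2 weeks after the last injection. The last injection is therefore at about Week 166, and the TEAE period ends at about Week 176.
- Death rate: the documents give none. I assume a constant 0.5 to 2 per 100 patient-years.

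**Step 1: scheduled gap between the two values.** 169 − 57 = 112 days = 16 weeks. 337 − 169 = 168 days = 24 weeks, and every later pair gives the same. This reproduces the protocol's 24-week interval. With the ±7-day windows the gaps are 14 to 18 weeks and 22 to 26 weeks.

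**Step 2: share of remaining TEAE follow-up inside the gap.** Share = gap / (176 − week of first low value).

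| First low value | Gap / remaining weeks | Share |
|---|---|---|
| Week 8 | 16/168 | 9.5% |
| Week 24 | 24/152 | 15.8% |
| Week 48 | 24/128 | 18.8% |
| Week 72 | 24/104 | 23.1% |
| Week 96 | 24/80 | 30.0% |
| Week 120 | 24/56 | 42.9% |
| Week 144 | 24/32 | 75.0% |

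In that share of follow-up, a death without a second sample excludes the patient. Treatment can end earlier, on commercial availability or in 2Q 2017, and the share then rises. For example, with EOT at Week 96 the TEAE period ends at about Week 104, and a first low value at Week 48 gives 24/56 = 42.9% instead of 18.8%.

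**Step 3: effect on a death rate.** Let h be the hazard, T the remaining follow-up and G the gap. Assume that every survivor of the gap is confirmed and that patient-years start at the first low value. Then:

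- deaths counted = exp(−hG) × [1 − exp(−h(T − G))]
- patient-years counted = exp(−hG) × {G + [1 − exp(−h(T − G))]/h}

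For small h the ratio of this rate to the true rate is close to (T − G)/T. First low at Week 8: 152/168 = 0.90. First low at Week 24: 128/152 = 0.84. The exact formula at h = 1 per 100 patient-years gives 0.904 and 0.840, and across 0.5 to 2 per 100 patient-years it gives 0.902 to 0.904 and 0.839 to 0.841. Counting from the second value, or admitting patients at the first, gives 1.00.

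In absolute terms, 1 − exp(−hG) is about 0.15% (h = 0.5 per 100 patient-years, 16 weeks) to 0.9% (h = 2 per 100 patient-years, 24 weeks) of patients with a first low value.

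**Step 4: patients who stop.** They should have an EOT-type visit with lipids, within 5 days if possible (Protocol 10.3.4 and 10.1.1.17), and unscheduled values may be used (SAP 2.1.3, 2.5.5). That sample can be the second value if it is <25 mg/dL, within last dose + 21 days and at least 21 days after the first. Only the first 20 days of the gap are too early: 20 of the 111 days between Weeks 8 and 24 (18%), or 20 of the 167 in a 24-week gap (12%).

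**Step 5: down-titrated patients.** They are left out only if the next value is ≥25 mg/dL. The documents give no frequency for this.

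**The case against.** The strongest defence is that two consecutive values are meant to capture sustained low LDL-C. A patient whose LDL-C has recovered no longer has that exposure, and a single value, which may be non-fasting, could be a transient low. This stands as a reason to keep the two-value subgroup. It does not justify starting the clock before membership can be known.

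A reader might infer that everyone who dies, stops or is down-titrated in the gap drops out. The documents do not support that. Stoppers are due a lipid sample that can confirm, and down-titrated patients who remain <25 mg/dL stay in. Nor does the subgroup contain only patients in whom nobody reacted.

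A reader might also take the shares in the table as the proportion of all fatal events lost. That is too strong. A TEAE that starts in the gap and leads to death after confirmation is counted, because SAP 2.4.5.2 includes TEAEs leading to death whenever the death occurs. Measuring only to Week 168 would overstate the shares, since TEAEs are collected to last dose + 70 days.

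Finally, no event is lost to the study. All TEAEs and deaths stay in the safety-population tables, and this subgroup is descriptive, with no test or comparator. That limits the consequence, but the overall tables cannot show whether events follow very low LDL-C.

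**Conclusion.** The mismatch between entry and start of counting is real. Exclusion is certain for death before a second qualifying sample and for a first low value that is the last sample. It is conditional for stopping and down-titration. The subgroup therefore understates deaths after a first low value, and to a lesser, unquantified degree discontinuations.

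The gap covers 9.5% to 75% of remaining TEAE follow-up, depending on when the first low value occurs; the largest shares apply only to patients first low late in the study. The rate ratios of about 0.90 (Week 8) and 0.84 (Week 24) rest on scheduled sampling, follow-up to about Week 176, a low constant hazard, confirmation of all survivors, and patient-years from the first low value. The SAP does not say where patient-years start in this subgroup. The documents give neither the number of patients expected to be low nor the timing of first low values, so no overall figure can be stated.

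The point does not touch the overall safety conclusions. It is worth correcting because this is the only planned table relating adverse events to very low LDL-C.

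**What to change.** In SAP 2.4.5.1:

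- Keep the two-consecutive-value subgroup, but count TEAEs and patient-years from the date of the second (confirming) value.
- Add a table for patients with at least one calculated LDL-C <25 mg/dL, counting TEAEs and patient-years from the date of that value.
- State whether the analysis windows in SAP Table 1 apply to the pair. SAP 2.1.5 carries over the LDL-C rules only where applicable. If the windows applied, a further 33% to 59% of the days in a gap would lie outside any window, and fewer EOT or unscheduled samples could confirm.

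The cost is SAP wording and one more set of tables from data already collected. The single-value table will include some transient lows, and the two-value table will omit events that occur before confirmation. Read together, the two tables cover both gaps.

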#### Analysis of all treatment-emergent adverse events

The following TEAE summaries will be generated:

- Overview of TEAEs, summarizing number (%) of patients with any
  - TEAE;
  - Serious TEAE;
  - TEAE leading to death;
  - TEAE leading to permanent treatment discontinuation.
- All TEAEs by primary SOC, HLGT, HLT, and PT
- Number (%) of patients experiencing common TEAE(s) presented by primary SOC, HLT and PT (HLT incidence ≥2 % in overall patients in the OLE), sorted by SOC internationally agreed order and by alphabetic order for the other levels (HLT and PT);
- All TEAEs by primary SOC and PT, sorted by the internationally agreed SOC order and by decreasing incidence of PTs within each SOC. This sorting order will be applied to all other tables by SOC and PT of TEAEs, unless otherwise specified;
- All TEAEs regardless of relationship in one column and, in the same table a second column with TEAEs related to alirocumab according to investigator's opinion by primary SOC, HLGT, HLT and PT;
- All TEAEs by maximal intensity (ie, mild, moderate or severe), presented by primary SOC and PT, sorted by the sorting order defined above;
- The event rate per patient-year (the number of patients with an event in question divided by total patient-years in OLE study) will be provided for all TEAEs by SOC and PT. For a patient with event, patient year is censored at time of first event in OLE; for patient without event, it corresponds to length of OLE TEAE period;
- Kaplan-Meier curves will be provided, when appropriate, for time from first dose of OLE study treatment to the first occurrence of selected TEAEs as well as incidence rates at 24, 52, 78, 104 and 156 weeks of exposure. Patients without any event will be censored at the end of the TEAE period. Selected TEAEs could be local injection site reactions, general allergic reactions, hepatic disorders, diabetes among non-diabetic patients at baseline, and TEAE related to any clinically significant signal that needs further characterization.

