### Analysis of all treatment emergent serious adverse event(s)

- All serious TEAEs by primary SOC, HLGT, HLT, and PT and by SOC/PT;
- All serious TEAEs regardless of relationship in one column and, in the same table a second column with TEAEs related to alirocumab according to investigator's opinion, by primary SOC, HLGT, HLT, and PT;
- The event rate per patient-year will be provided for all serious TEAEs by SOC and PT.

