# Analysis of groupings of adverse events including selected adverse events of special interest

All grouping of TEAEs including adverse events of special interest as listed in Section 2.1.4.1 will be analyzed using selections defined in Section 2.1.4.1 and will be presented by SMQ and PT (when selection is based on SMQs) and by SOC and PT (when selection is based on the e-CRF tick box or HLGT/HLT). The summaries will be sorted by decreasing incidence of PT within each SOC/SMQ.

- Analyses of grouping of AEs for diabetes will be performed overall and according to the diabetic status at baseline.
- Serious TEAEs by PT for each grouping of AEs of special interest;
- TEAE(s) leading to permanent treatment discontinuation by PT for each grouping of AEs of special interest.

In addition, the following variables will be tabulated for the local injection site reactions TEAEs:

- Intensity of the event (mild, moderate, severe);
- Number of events divided by the number of OLE IMP injections received;
- Time from first OLE IMP injection to first injection site reaction;
- Description of the highest intensity of each symptom recorded in the specific e-CRF page with table and bar chart.

Besides, description of symptoms and possible etiologies for General Allergic Reaction TEAE reported by investigator (using the tick box), will be presented.

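### The subgroup with two LDL-C values below 25 mg/dL counts only TEAEs from the first low value, but no rule moves the start of time at risk or injection counts from the first OLE dose

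*SAP*

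**What the plan says.** The subgroup paragraph of SAP 2.4.5.1 applies to patients with two consecutive calculated LDL-C values below 25 mg/dL, which SAP 2.1.5 requires to be at least 21 days apart. If applicable, "similar summaries of TEAEs as those described above will be also provided on the safety subgroup population". The paragraph then narrows the events: only TEAEs that clearly or possibly "occurred, worsened or became serious the day or after the first level of LDL-C <25 mg/dL will be considered". It does not list which summaries carry over, and it gives no start of time at risk.

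The summaries it refers back to include these:

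- **Patient-year rates for all TEAEs.** One rule covers patients who have the event: "For a patient with event, patient year is censored at time of first event in OLE". Those who never have it contribute the whole period, since "for patient without event, it corresponds to length of OLE TEAE period". SAP 2.1.4 starts the TEAE period at the first OLE dose and ends it 70 days after the last.
- **The same rates for serious events.** "The event rate per patient-year will be provided for all serious TEAEs by SOC and PT".
- **Kaplan-Meier curves, when appropriate.** These are "for time from first dose of OLE study treatment to the first occurrence of selected TEAEs", with "incidence rates at 24, 52, 78, 104 and 156 weeks of exposure".
- **Local injection site reactions.** One measure is "Number of events divided by the number of OLE IMP injections received". Another is the time from the first OLE injection to the first reaction.

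SAP 2.1.5 and 2.4.6 derive and analyse the time from first OLE dose to the first low value, but as a separate endpoint. Neither section links that date to the subgroup's TEAE summaries.

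**The concern.** By excluding events before the low value, the SAP shows that it wants to describe what happens after LDL-C has become very low. A rate with that numerator needs a denominator covering the same period. If the main definitions are reused unchanged, each subgroup patient also contributes time and injections from before the low value, when no clearly dated event can count. The first scheduled lipid sample after the first OLE dose is at Week 8 (Protocol 1.2 and 10.1.1.3). At scheduled visits, each patient therefore brings about 8 weeks or more of such time.

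Safety is the study's primary objective, and this paragraph holds the SAP's TEAE summaries for patients with very low LDL-C. Diluted rates and delayed Kaplan-Meier curves would make the period after the low value look safer than it was.

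**Working it through.** The plan gives no figure for this subgroup, so there is nothing to reproduce. The check applies the SAP's own definitions to a patient whose first low value is at week t.

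**Inputs from the documents**

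- Treatment lasts up to 168 weeks, and the EOT visit is 2 weeks after the last injection (Protocol 6.1 and 6.2.1). The last injection is then at Week 166.
- The TEAE period ends 10 weeks after the last dose, so T = 166 + 10 = 176 weeks.
- Injections are every 2 weeks from Week 0 to Week 166: 166/2 + 1 = 84.
- A visit-day injection follows the blood sample (Protocol 8.1.2), so t/2 injections precede the first low value.
- Lipids are scheduled after the first dose at Weeks 8, 24 and 48, then every 24 weeks (Protocol 1.2).

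**Assumptions**

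- The documents do not give the timing of low values. I use t = 8, 24 and 48.
- Where an event rate is needed, I assume 0.20 per year after the low value, with 52.18 weeks per year.
- TEAEs of unclear timing are left out.
- Events before the low value do not end time at risk.

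**1. Patient-year rate, rare event.** The counted events are the same, but the denominator is T instead of T − t. The rate is understated by t/T.

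**2. Patient-year rate at 0.20 per year.** Expected time from the low value to the first counted event or end of follow-up is m = (1 − exp(−0.20(T − t)))/0.20, with times in years. The ratio of the rate as defined to the restarted rate is m/(t + m):

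- t = 8: 2.374/(0.153 + 2.374) = 0.939
- t = 24: 2.208/(0.460 + 2.208) = 0.828
- t = 48: 1.939/(0.920 + 1.939) = 0.678

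**3. Reactions per injection.** The share of injections before the low value is (t/2)/84, whatever the pattern of reactions after it.

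| Understated by | t = 8 | t = 24 | t = 48 |
|---|---|---|---|
| Rare event, T = 176 | 8/176 = 4.5% | 24/176 = 13.6% | 48/176 = 27.3% |
| 0.20 per year, T = 176 | 6.1% | 17.2% | 32.2% |
| Per injection, 84 injections | 4/84 = 4.8% | 12/84 = 14.3% | 24/84 = 28.6% |

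Follow-up can be shorter, because treatment ends with commercial availability or the 2017 closing date. For 104 treatment weeks, T = 102 + 10 = 112 and there are 52 injections. The rare-event shortfall is then 7.1%, 21.4% and 42.9%, and the per-injection shortfall 7.7%, 23.1% and 46.2%.

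**4. Kaplan-Meier at 0.20 per year.** Counted from first dose, the value at week L is 1 − exp(−0.20(L − t)/52.18), or 0 if L ≤ t. Counted from the low value it is 1 − exp(−0.20L/52.18).

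| Readout | From low value | From first dose, t = 8 | t = 24 | t = 48 |
|---|---|---|---|---|
| 24 weeks | 8.8% | 5.9% | 0% | 0% |
| 52 weeks | 18.1% | 15.5% | 10.2% | 1.5% |
| 156 weeks | 45.0% | 43.3% | 39.7% | 33.9% |

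In relative terms, the early readouts are lowered most.

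**5. Time between the two low values.** Subgroup membership needs a second low value, which at scheduled visits comes 16 weeks after the first (Week 8 to Week 24) or 24 weeks after it (later pairs). A patient who dies in between cannot enter. With t = 8, restarting at the first low value leaves 16 of the remaining 176 − 8 = 168 weeks (9.5%) in which no death is possible.

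**The case against.** The strongest defence is that this is an open specification rather than an error. The paragraph applies only if applicable and promises similar, not identical, summaries. It already changes the event window, so a programmer could sensibly move the start date as well, and that date is already derived. Most of the summaries are n (%) tables with no exposure denominator. Kaplan-Meier is produced only when appropriate, the subgroup is descriptive and no decision rule uses it. This stands and sets the severity. It does not close the gap: the text fixes a new numerator, and every denominator it refers back to starts at the first dose.

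Counting TEAEs of unclear timing pushes the rates up and partly offsets the dilution. That also stands, though its size is unknown.

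Four stronger readings are tempting, and the documents do not support them.

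- **That the SAP commits to the mismatched denominators.** It does not say which summaries carry over, so the bias is conditional on reuse as defined.
- **That the error could be nil or upward, because patient-years stop at the first event in the OLE.** An uncounted early event would have to end a patient's time at risk while a later event in the same patient still counted. The rate concerns the event in question, and the subgroup paragraph considers only qualifying TEAEs. The natural reading is that the counted event stops the clock, and then the error is downward.
- **That an interim analysis would enlarge the problem by a known amount.** SAP section 3 only allows for interim analyses and names no cut-off week.
- **That Kaplan-Meier time from first dose is wrong in itself.** The readouts are labelled as weeks of exposure, which is a different quantity from time since the low value. They mislead if read as risk after the low value, and the event restriction invites that reading.

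**Conclusion.** The concern holds, as a minor point. The subgroup's event window starts at the first low value, while the patient-year, Kaplan-Meier and injection-site measures it refers back to start at the first OLE dose or injection. Produced as defined, those outputs are biased downward. With full follow-up and a first low value at Week 8, the shortfall is about 5% for rare-event rates and for reactions per injection. It grows with a later low value or shorter follow-up.

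All sizes are illustrations: the timing of low values, the event rate and the follow-up lengths in the population are not in the documents. The direction assumes that TEAEs of unclear timing do not outweigh the dilution. The n (%) tables and the main safety analyses are unaffected.

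**What to change.** Amend the subgroup paragraph of SAP 2.4.5.1 in one of two ways.

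**Option 1.** Limit the subgroup to n (%) tables.

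**Option 2.** List the summaries that apply and state the following:

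- For any patient-year rate, Kaplan-Meier output or time to first injection site reaction, time starts at the date of the first calculated LDL-C below 25 mg/dL of the qualifying pair. It ends at the first counted TEAE or the end of the TEAE period. Fixed-week readouts are counted from that start.
- Reactions per injection are divided by all injections given on or after that date.
- Uncounted events before the low value do not end time at risk.
- A date rule applies to TEAEs of unclear timing. SAP 2.5.3 imputes AE dates for categorization only, so it supplies no date for these analyses.
- Survival between the first and the confirming low value is guaranteed by the entry rule. For fatal events, start time at the confirming value or add that as a sensitivity analysis.

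The cost is a few SAP sentences and, for the second option, a changed start date in the rate, Kaplan-Meier and injection-site programs. The first-low date is already needed for SAP 2.1.5 and 2.4.6, and no new data are required.
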